### Performance evaluation criterias

| Extracorporeal life support system with pulmonary and / or heart failure |
|---|
| Primary results  |

|                          |   |
|--------------------------|---|
| 1                 | Cytokine response [Time: 24-48 hours]

The level of pro- and anti-inflammatory cytokines (IL-1, IL-6, IL-8, IL-10, tumor alpha-factor) before the implantation, 2 hours after the start of ECMO support, explantation of ECMO, 24 hours after explantation of ECMO.     |
| 2                 | SOFA-Score [Time Frame: 24, 48, 72 hours]

Sequential Organ Failure Assessment Score at 24, 48, 72 h (values from 6 to 24, where the higher values explain higher disease severity)   |
| 3                 | Difference of mean arterial pressure [Time Frame: 24, 48, 72 hours]

Comparison of mean arterial pressure at 24, 48, 72 hours between between two interventions (CytoSorb and Jafron)   |
| 4                 | Difference of CVP [Time Frame: 24, 48, 72 hours]

Comparison of CVP at 24, 48, 72 hours between between two interventions (CytoSorb and Jafron)   |
| 5                 | Serum lactate [ Time Frame: 24, 48, 72 hours ]

Level of serum lactate at 24, 48, 72 h  |
| 6                 | 
 
Days on ventilator, vasopressor and renal replacement therapy [ Time Frame: until day 30 post-surgery ]
 

Total days on ventilator, vasopressor and renal replacement therapy within 30 days post-surgery will be assessed |
| 7                 | Doses of vasopressors and / or inotropes ( $\mu\text{g} / \text{h} / \text{kg}$ bodyweight) [Time: first 72 hours]  |
| Secondary results |   |
| 1                 | Inflammatory response - The level of C-reactive protein (CRP) [Time: 24-48 hours]

The level of C-reactive protein (CRP) before the start of ECMO, 2 hours after the implantation of ECMO, during ECMO, 24 hours after ECMO explantation.                        |
| 2                 | Inflammatory response - The level of leukocytes [Time: 24-48 hours]

The level of leukocytes before the start of ECMO, 2 hours after the implantation of ECMO, during ECMO, 24 hours after ECMO explantation.   |

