| 3                 | Inflammatory response - The level of procalcitonin [Time: 24-48 hours]

The level of procalcitonin before the start of ECMO, 2 hours after the implantation of ECMO, during ECMO, 24 hours after ECMO explantation.   |
| 4                 | Level of leukocyte [Time: 24-48 hours]

Level of leukocyte cells in the bloodstream at 24, 48 hours.  |

|                          |  |
|--------------------------|--|
| 5                 | Application and dosage of vasopressors [Deadline: first 48 hours]
Incidence of application and level of dosage of vasopressors on days 2 and 3 after surgery; |
| 6                 | Application and dosage of inotropes [Deadline: first 48 hours]
Incidence of application and level of dosage of inotropes on days 2 and 3 after surgery;       |
| Long-term results |  |
| 1                 | Length of stay in the intensive care unit [Duration: first 48 hours]   |
| 2                 | Length of hospital stay [Term: up to 1 month];   |
| 3                 | 30 day survival rate.  |

| Patients with left ventricular assist device implantation |  |
|--|--|
| Primary results   |  |
| 1   | Difference of Cytokine response [Time: 24-48 hours]
Level of pro- and anti-inflammatory cytokines (IL-1, IL-6, IL-8, IL-10, tumor necrosis factor-alfa, procalcitonin)  |
| 2   | Doses of vasopressors and / or inotropes ( $\mu$ g / h / kg bodyweight)
[Deadline: first 72 hours]  |
| 3   | Renal function [Time: first 72 hours] creatinine level   |
| 4   | Lactate level [Time: first 72 hours]   |
| Secondary results   |  |
| 1   | Inflammatory response - The level of C-reactive protein (CRP) [Time: 24-48 hours]
The level of C-reactive protein (CRP) before the start of the operation, 2 hours after the start of the operation, when the operation is turned off, 24 hours after the shutdown of the operation |
| 2   | Inflammatory response - The level of leukocytes [Time: 24-48 hours]
The level of leukocytes before the start of the operation, 2 hours after the start of the operation, when the operation is turned off, 24 hours after the shutdown of the operation                             |

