| 3   | Inflammatory response - The level of procalcitonin [Time: 24-48 hours]
The level of procalcitonin before the start of the operation, 2 hours after the start of the operation, when the operation is turned off, 24 hours after the shutdown of the operation                       |

|                          |  |
|--------------------------|--|
| 4                 | Application and dosage of vasopressors [Deadline: first 48 hours]
Incidence of application and level of dosage of vasopressors on days 2 and 3 after surgery; |
| 5                 | Application and dosage of inotropes [Deadline: first 48 hours]
Incidence of application and level of dosage of inotropes on days 2 and 3 after surgery;       |
| Long-term results |  |
| 1                 | Length of stay in the intensive care unit [Duration: first 48 hours]   |
| 2                 | Length of hospital stay [Term: up to 1 month];   |
| 3                 | 30 day survival rate.  |

| For operations with prolonged cardio pulmonary bypass, hypothermia and circulatory arrest |  |
|--|--|
| Primary results   |  |
| 1   | Cytokine response [Time: 24-48 hours]
Difference of Cytokine response [Time: 24-48 hours]
Level of pro- and anti-inflammatory cytokines (IL-1, IL-6, IL-8, IL-10, tumor necrosis factor-alfa, procalcitonin, C-reactive protein) |
| 2   | SOFA-Score [Time Frame: 24, 48, 72 hours]
Sequential Organ Failure Assessment Score at 24, 48, 72 h (values from 6 to 24, where the higher values explain higher disease severity)  |
| 3   | Difference of mean arterial pressure [Time Frame: 24, 48, 72 hours]
Comparison of mean arterial pressure at 24, 48, 72 hours between between two interventions (CytoSorb and Jaftron)   |
| 4   | Difference of CVP [Time Frame: 24, 48, 72 hours]
Comparison of mean arterial pressure at 24, 48, 72 hours between between two interventions (CytoSorb and Jaftron)  |
| 5   | Level of Serum lactate [ Time Frame: 24, 48, 72 hours ]
Comparison of mean arterial pressure at 24, 48, 72 hours between between two interventions (CytoSorb and Jaftron)   |
| Secondary results   |  |
| 1   | Inflammatory response - The level of C-reactive protein (CRP) [Time: 24-48 hours]
The level of C-reactive protein (CRP) before the cardiopulmonary bypass 2 hours   |

|                          |  |
|--------------------------|--|

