### Statistical research

- 1) statistical data processing
- 2) comparison and analysis of initial data

After data acquisition, statistical analysis will be performed using SPSS Statistics version 22. For quantitative data, the nonparametric Mann-Whitney U test and parametric t-test will be performed, and for qualitative studies, the nonparametric Fisher's exact test and the parametric  $\chi^2$  test will be performed. Also, logistic regression for categorical outcomes and survival analyzes (non-parametric Kaplan-Meyer and parametric Cox regression) will be performed.

**Age:** 18 years and older

**Gender:** All

**Inclusion of healthy volunteers:** Not

| Groups  | Inclusion criteria   | Exclusion criteria  |
|--|---|--|
| Patients on an extracorporeal life support system with heart failure                             | 
 
• Implantation of intravenous ECMO
 
• Hemodynamic support with vasopressors and / or tonics;
 
• Procalcitonin level <math>\geq 1</math> ng / ml;
 
• Invasive hemodynamic monitoring;
 
• Written informed consent.
 
   | 
 
• Age less than 18 years old
 
• Terminal hepatic or renal failure just before the procedure
 
• Patient's written refusal to participate in the study
 
 |
| Patients on an extracorporeal life support system with pulmonary failure                         | 
 
• IV ECMO implantation
 
• High levels of venous and arterial CO2 (CO2 > 50 mmHg),
 
• Low paO2, SvO2, SpO2.
 
• Invasive hemodynamic monitoring;
 
• Written informed consent.
 
                                     | 
 
• Age less than 18 years old
 
• Terminal hepatic or renal failure just before the procedure
 
• Patient's written refusal to participate in the study
 
 |

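### No deciding primary outcome is named: the three outcome tables list 7, 4 and 5 unranked primary rows, with no time point, significance level or multiplicity rule to choose between them

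*Combined protocol and SAP*

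**What the plan says.** The section Performance evaluation criterias has three tables, each with its own block of primary results.

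- **ECMO:** 7 rows (cytokines; SOFA; mean arterial pressure; CVP; lactate; days on ventilator, vasopressor and renal replacement; vasopressor/inotrope dose).
- **LVAD:** 4 rows (cytokines; vasopressor/inotrope dose; creatinine; lactate).
- **Prolonged bypass:** 5 rows by label (cytokines; SOFA; mean arterial pressure; CVP; lactate). The descriptions under CVP and lactate both speak of mean arterial pressure and need correcting.

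No row is ranked. Rows 2-5 of the ECMO and bypass tables each name three times, for example "SOFA-Score [Time Frame: 24, 48, 72 hours", and none is marked as deciding.

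Some variables sit in two tiers:

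- **Procalcitonin:** in LVAD primary row 1 ("Level of pro- and anti-inflammatory cytokines (IL-1, IL-6, IL-8, IL-10, tumor necrosis factor-alfa, procalcitonin") and LVAD secondary row 3 ("The level of procalcitonin before the start of the operation, 2 hours after the start of the operation"). The bypass table does the same.
- **CRP:** in bypass primary row 1 ("tumor necrosis factor-alfa, procalcitonin, C-reactive protein") and bypass secondary row 1 ("The level of C-reactive protein (CRP) before the cardiopulmonary bypass 2 hours").
- **Vasopressor/inotrope dose:** "Doses of vasopressors and / or inotropes" is primary over the first 72 hours for ECMO and LVAD. The secondary rows cover "Incidence of application and level of dosage of vasopressors on days 2 and 3 after surgery", with a matching row for inotropes. Those rows are headed first 48 hours but described as days 2 and 3.

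The section Statistical research states "For quantitative data, the nonparametric Mann-Whitney U test and parametric t-test will be performed" and lists further tests. It gives no significance level, ranking, co-primary rule or multiplicity control. Some pages between section 4 and section 8 were not available for this review.

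**The concern.** With several equal primaries and no rule, a reader of the results cannot tell the planned answer from one chosen after the data were seen. The setting leaves room for that choice: the trial is unmasked, and section 8 starts analysis in 2022 while recruitment continues into the third year. Section 8 (item 7) also promises to identify an effective method, and section 9 says the resulting methods will become standards and recommendations. Nothing says which outcome supports either claim.

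Cytokines add a further problem. They are primary row 1 in every table. Yet section 4, as worded, has cytokine and complement levels determined only if the investigators find a corresponding difference in clinical variables. A primary outcome that is measured only when another comparison looks different is not a prespecified primary.

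**Working it through.** The plan gives no significance level or error rate, so there is no figure of its own to reproduce.

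**Inputs from the documents.** Primary rows k = 7 (ECMO), 4 (LVAD) and 5 (bypass). Patients per arm, from section 4: ECMO 10 + 10 = 20, LVAD 5, bypass 25.

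**Assumptions.** Two-sided 0.05 per row, one test per row, no device difference on any row, equal correlation between rows within a table.

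**Step 1: by row.** If independent, the chance of at least one false positive is 1 − 0.95^k. If correlated, it is 1 − P(all |Z| < 1.96) for equicorrelated normal statistics, by numerical integration.

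| Table | k | Independent | Correlation 0.5 | Correlation 0.9 |
|---|---|---|---|---|
| ECMO | 7 | 1 − 0.95^7 = 30.2% | 23.0% | 11.4% |
| Bypass | 5 | 1 − 0.95^5 = 22.6% | 18.3% | 10.2% |
| LVAD | 4 | 1 − 0.95^4 = 18.5% | 15.6% | 9.4% |

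**Step 2: LVAD with the exact Mann-Whitney test.** At 5 v 5 there are 252 rank allocations. Rejecting at U ≤ 2 in either tail gives 8/252 = 3.17%; U ≤ 3 would give 14/252 = 5.56%, which is over 5%. So the true size is 3.17%. Four rows give 1 − (1 − 0.0317)^4 = 12.1% if independent, 10.3% at correlation 0.5 and 6.2% at 0.9.

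**Step 3: what one test per row leaves out.**

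- *Counting named variables.* ECMO: 5 cytokines + SOFA + MAP + CVP + lactate + 3 day-counts + dose = 13. LVAD: 6 + 3 = 9. Bypass: 7 + 4 = 11. In the order ECMO / LVAD / bypass, the chance is 49 / 37 / 43% if independent, 33 / 27 / 30% at correlation 0.5 and 14 / 12 / 13% at 0.9.
- *Counting rows with the three stated times.* ECMO: 4 × 3 + 3 = 15 comparisons, 1 − 0.95^15 = 54% if independent. Bypass: 4 × 3 + 1 = 13 comparisons, 49%. By simulation with correlation 0.5 between outcomes and 0.8 across times, about 32-33% and 29%. With 0.9 and 0.95, 14% and 13%.

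**Step 4: power (t-test, 80%, two-sided).**

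| Table | One primary at 0.05 | Bonferroni on the present list |
|---|---|---|
| ECMO, 20 v 20 | 0.91 SD | 1.17 SD (0.05/7) |
| Bypass, 25 v 25 | 0.81 SD | 1.00 SD (0.05/5) |
| LVAD, 5 v 5 | 2.02 SD | not computed |

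These are differences detectable on one given row. The chance of detecting at least one row is a different quantity. Put a true difference of 0.91 SD (ECMO) or 0.81 SD (bypass) on every row and apply Bonferroni. By simulation, at least one row is then significant in about 99% (independent), 89% (correlation 0.5) or 70% (0.9) of ECMO trials, and 99, 89 or 72% of bypass trials. A single named primary has 80%. If only one row truly differs, Bonferroni power on that row is 52% (ECMO) or 57% (bypass).

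**The case against.** **The outcomes are correlated and the 5% is assumed.** Both are true. Correlation lowers the figures, but at 0.9 the ECMO and bypass tables still run at about twice 5%. Only LVAD with the exact Mann-Whitney test comes close to nominal, at 6%. The plan states no level, so one has to be assumed.

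**The work is exploratory.** The tasks in section 2.3 speak of assessing and studying, and no confirmatory hypothesis is written. But the plan does not call itself exploratory, and sections 8 and 9 promise conclusions that need a deciding outcome.

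**Stronger readings the documents do not support:**

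- *A single trial-wide error rate.* Combining all 16 rows gives 56% (independent), 47% (0.5) or 28% (0.9). That applies only if a positive row in any table counts as success for the trial. Section 2.3 sets separate tasks for the three populations, and no rule joins the tables.
- *The section 4 condition contradicts the sampling schedule.* Section 8 schedules blood sampling in all populations, while section 4 conditions the determination of levels. Sampling everyone and assaying conditionally satisfies both. The clear conflict is with cytokines as primary row 1. The sentence is awkward English, so its intent is uncertain.
- *Naming two tests doubles the error.* The plan pairs parametric and nonparametric methods throughout, which may mean a choice by distribution. Accepting either test adds only about 1-2 points per comparison at 20-25 per arm. This is minor.
- *One primary always has more power than a corrected list.* Step 4 shows this holds for a given row. For finding at least one of several true effects, it depends on how many rows differ and on their correlation.

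**Conclusion.** The point stands. The available text gives 7, 4 and 5 unranked primary rows and no deciding outcome, time point, significance level or multiplicity rule.

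As listed and tested by row, ECMO carries an 11-30% chance of at least one false primary and bypass 10-23%. LVAD carries 9-19%, or 6-12% with the exact Mann-Whitney test. These ranges run from correlation 0.9 to independence and rest on the Step 1 assumptions. They rise if each analyte and time point is tested separately.

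The tier overlaps are real for procalcitonin (LVAD, bypass) and CRP (bypass). For vasopressor/inotrope dose (ECMO, LVAD) the overlap is partial, because the secondary rows add incidence of use and carry their own conflicting windows. The condition on cytokine determination must be reconciled with cytokines being primary. All of this needs settling before analysis, since a primary chosen afterwards would not be credible.

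**What to change.** Before analysis:

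1. Name one primary outcome, one time point and one test. Do this for the whole device comparison, or once each for the ECMO and bypass tables, stated to be separate questions. SOFA at 72 hours is one candidate already listed in both tables. State the significance level and how deaths before the time point are scored. Alternatively, if several primaries are kept, declare a multiplicity procedure such as Holm.
2. Make the other rows secondary, with Holm adjustment or with estimates and 95% confidence intervals and no significance claims.
3. Put procalcitonin, CRP and vasopressor/inotrope dose in one tier each per table. Reconcile the 48-hour heading with days 2 and 3, and correct the bypass CVP and lactate descriptions.
4. Report LVAD (5 v 5) descriptively.
5. Assay cytokines in all patients, or label them exploratory.

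The cost is wording, with no new patients or visits. Blood sampling is already scheduled, so removing the condition in section 4 adds at most assay cost. The downside is that most present primary rows lose confirmatory status. LVAD would have no confirmatory test, but at 5 v 5 it reaches 80% power only for a difference of about 2 SD.

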## 2.3. Objectives of the program.

### **Task 1. Assessment the results of the use of extracorporeal life support systems in the treatment of pulmonary and / or heart failure.**

Subtask 1.1. Assessment of the restoration of organ function during extracorporeal life support systems using extracorporeal hemocorrection.

Subtask 1.2. Assessment of the normalization of the body's immune response and restoration of organ function during extracorporeal life support systems using an extracorporeal cytokine adsorber.

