### **Task 4. Studying the restoration of organ function during operations in conditions of the long-term cardiopulmonary bypass.**

Task 4.1. Assessment of the restoration of organ function during operations with long-term cardiopulmonary bypass, hypothermia and circulatory arrest, with the use of extracorporeal hemocorrection.

Task 4.2. Assessment of the restoration of organ function during operations with long-term cardiopulmonary bypass, hypothermia and circulatory arrest using an extracorporeal cytokine adsorber.

**Task 5. Improvement of the method of implantation of organ-replacing technologies to reduce complications in the treatment of heart and pulmonary failure.**

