#### **4. Research methods and ethical issues.**

All patients admitted to Non-profit JSC “NRCCS” who meet the study criteria (patients on an extracorporeal life support system, mechanical circulatory support, surgery on the aortic arch) will be included in the study after obtaining a signed informed consent. Participants will be randomized into 2 groups in a 1: 1 division.

**Intervention team # 1** using an extracorporeal hemoperfusion device Jaftron (Zhuhai Jaftron Biomedical, China) (50 patients) in subgroups: A (n = 10) - patients on extracorporeal life support systems with heart failure; B (n = 10) - patients on extracorporeal life support systems with pulmonary failure; C (n = 5) - patients with implantation of a left ventricular accessory device; D (n = 25) - during operations with prolonged artificial circulation, hypothermia and circulatory arrest.

**Intervention team # 2** using extracorporeal cytokine, CytoSorb (CytoSorbents Corporation, Monmouth Junction, NJ, USA) (50 patients) in subgroups: A (n = 10) - patients on extracorporeal life support systems in heart failure; B (n = 10) - patients on extracorporeal life support systems with pulmonary failure; C (n = 5) - patients with implantation of a left ventricular accessory device; D (n = 25) - during operations with prolonged artificial circulation, hypothermia and circulatory arrest.

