#### **Retrospective analysis of patients who received a fully artificial heart.**

The duration of the intervention in each group will be 72 hours. Each Jaftron / CytoSorb Removal Column can be used within 24 hours, so all patients in 2 groups use 3 filters during the study.

Researchers will collect demographic, clinical and laboratory data from patients before, during and after surgery.

The incidence of early cellular or humoral rejection, the duration of ventilation, intensive care and hospital stay, the use of vasopressors and inotropes in the perioperative period, and the incidence of perioperative complications and survivals will be documented.

The level of cytokines (IL-1, IL-6, IL-8, IL-10, tumor necrosis factor alpha) and complements will be determined before, during and after the use of the extracorporeal life support system for heart and pulmonary failure; surgery on the aortic arch, patients on mechanical circulatory support, if investigators find a corresponding difference between the two groups in terms of clinical variables.

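### SOFA, a primary result for 90 of the 100 patients, has no score before device start and no baseline-adjusted analysis, and its stated minimum of 6 is unexplained

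*Combined protocol and SAP*

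**What the plan says.** All references are to the Combined protocol and SAP.

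- **Outcome and times.** Under Performance evaluation criterias, row 2 of the primary results is the same for the ECMO group and the prolonged-bypass group: SOFA at 24, 48 and 72 h, described as "values from 6 to 24, where the higher values explain higher disease severity". No earlier time is listed. The LVAD group has no SOFA outcome.
- **Objectives.** Section 2.3, Subtask 1.1 reads "Assessment of the restoration of organ function during extracorporeal life support systems using extracorporeal hemocorrection". Task 4.1 begins "Assessment of the restoration of organ function during operations with long-term cardiopulmonary bypass, hypothermia and circulatory arrest".
- **Baselines elsewhere.** The ECMO cytokine row in the same table has a pre-treatment sample: "before the implantation, 2 hours after the start of ECMO support, explantation of ECMO, 24 hours after explantation of ECMO". CRP, leukocytes and procalcitonin also have a sample before ECMO or bypass.
- **General data collection.** Section 4 adds "Researchers will collect demographic, clinical and laboratory data from patients before, during and after surgery", without naming SOFA or its inputs.
- **Allocation and size.** "Participants will be randomized into 2 groups in a 1: 1 division". Each arm has 10 ECMO patients with heart failure, 10 with pulmonary failure, 5 LVAD patients, and "D (n = 25) - during operations with prolonged artificial circulation, hypothermia and circulatory arrest".
- **Analysis.** Statistical research plans Mann-Whitney or t-tests for quantitative data. It mentions comparing initial data but names no variable, and gives no change score or baseline-adjusted model.

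**The concern.** Restoration is movement from a starting state. SOFA is the organ-function score among the primary results, yet it is first recorded 24 h in. The scheduled scores can show which arm is lower at 72 h, but not how far any patient has recovered since the device was started. With arms this small, the groups may also differ in starting severity by chance, and without a starting SOFA that difference can be neither seen nor removed on the same scale.

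The range is a second, smaller matter. The only scoring information given for this outcome starts at 6, and the components are not listed. If 6 became a data-entry limit, patients who recover well would be pushed up to it or rejected, and differences between devices would shrink where recovery shows.

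**Working it through.** The documents give no alpha, power, effect size, SD or sample-size calculation, so there is no figure of the plan's own to reproduce. The inputs taken from the plan are the arm sizes, the SOFA times, the stated range and the planned tests. Assumed: two-sided alpha 0.05, 80% power for detectable differences, and the SDs, means and baseline correlations (rho) shown.

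**1. Patients affected.** ECMO: 2 × (10 + 10) = 40. Bypass: 2 × 25 = 50. Total 90 of 100. One outcome table covers both ECMO subgroups, so ECMO is taken as 20 per arm.

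**2. Chance imbalance at baseline.** SE of the difference in starting means = SD × √(2/n).

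- n = 25: √(2/25) = 0.283 SD. An imbalance of at least 0.5 SD in either direction has z = 0.5/0.283 = 1.77, about 8% of trials.
- n = 20: √(2/20) = 0.316 SD; z = 0.5/0.316 = 1.58, about 11% of trials.

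**3. Value of a baseline covariate.** Detectable difference = (1.960 + 0.842) × SD × √(2/n). ANCOVA multiplies the SD by √(1 − rho²). An unadjusted change score multiplies it by √(2(1 − rho)).

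| n per arm | rho | Post score only | ANCOVA | Unadjusted change |
|---|---|---|---|---|
| 25 | 0.3 | 0.79 SD | 0.76 SD | 0.94 SD |
| 25 | 0.5 | 0.79 SD | 0.69 SD | 0.79 SD |
| 25 | 0.7 | 0.79 SD | 0.57 SD | 0.61 SD |
| 20 | 0.3 | 0.89 SD | 0.85 SD | 1.05 SD |
| 20 | 0.5 | 0.89 SD | 0.77 SD | 0.89 SD |
| 20 | 0.7 | 0.89 SD | 0.63 SD | 0.69 SD |

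Power for a true difference of 0.8 SD at rho 0.5:

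- n = 25: unadjusted 0.8/0.283 − 1.96 = 0.87, giving 81%. ANCOVA 0.8/(0.283 × 0.866) − 1.96 = 1.31, giving 90%.
- n = 20: unadjusted 72%, ANCOVA 83%.

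If the two ECMO subgroups were analysed separately (10 per arm), the figures would be 43% and 54%.

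**4. The range.** If six organs each score 0 to 4, the total runs from 6 × 0 = 0 to 6 × 4 = 24. If each scores 1 to 4, it runs from 6 to 24. So the stated maximum fits six organs at up to 4 points, and the stated minimum then needs every organ to score at least 1. Against a 0 to 24 scale, a minimum of 6 removes 6 of 25 possible values. The component scoring is an assumption, since the documents do not give it.

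**5. Effect if 6 were enforced as a floor.** Simulated scores: normal, rounded, held within 0 to 24, SD 3.5, arm means 3 points apart before rounding and limits. Scores of 0 to 5 are recorded as 6, with the planned Mann-Whitney test and 3,000 runs per scenario. Differences shown are for n = 25.

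| Arm means | Difference, no floor → floor | Power, n = 25 | Power, n = 20 |
|---|---|---|---|
| 12 v 9 | 2.96 → 2.66 | 82% → 82% | 73% → 72% |
| 9 v 6 | 2.96 → 1.99 | 83% → 78% | 72% → 68% |
| 7 v 4 | 2.82 → 1.35 | 82% → 71% | 71% → 59% |

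The loss is negligible in very sick patients and grows as they recover. Power falls less than the point difference because flooring also shrinks the spread.

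**The case against.** The strongest reply is that the arms are randomised, so comparing SOFA at 24, 48 and 72 h is valid without a baseline. Chance imbalance is already part of the test's error rate, and a baseline adds precision without being a condition of validity. This stands. A reader might infer that restoration of organ function cannot be measured at all, and the documents do not support that. The between-arm comparison bears on it. Lactate and mean arterial pressure are primary results in both groups, and the ECMO group adds vasopressor and inotrope dose and days on organ support. A baseline score might also be built from the pre-surgery data, although the plan does not promise this.

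A reader might also infer that recovered patients cannot be scored, or that the documents prove the range should start at 0. Neither follows. The range is a descriptive parenthesis. The plan contains no SOFA form, recoding rule or entry check, and it lists no components. If staff use the instrument's own score sheet, the data are unaffected. The minimum may simply be a slip: in the bypass table, the CVP and lactate rows are both described as comparisons of mean arterial pressure.

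Finally, redefining the outcome as an unadjusted change score could do harm. Below rho 0.5 it is less precise than the present plan, with a detectable difference of 0.94 against 0.79 SD at rho 0.3 and 25 per arm. That also stands, and it determines the form of the fix.

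**Conclusion.** The point holds in a limited form. For 90 of 100 patients, a primary result on organ function has no scheduled starting value and no baseline-adjusted analysis. Within-patient restoration on SOFA is therefore undefined, and chance imbalance in starting SOFA cannot be adjusted for. The trial's comparison of the two devices remains valid.

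The cost is mainly precision: at rho 0.5, 9 percentage points of power for 0.8 SD at 25 per arm and 11 at 20 per arm. The gain is smaller at rho 0.3 and larger at 0.7. The correlations, alpha and effect size are assumptions.

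The minimum of 6 is unexplained and needs reconciling with the components. Any harm from it depends on its being enforced as a limit, and on how many patients would score below 6. Nothing in the documents settles either.

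**What to change.** 1. In both SOFA rows of Performance evaluation criterias, state the components and the points per organ, and correct the minimum to match the named instrument so that a normal organ has a valid score. Any data-entry check should use the reconciled range.
2. Add a SOFA score before device start (for bypass patients, before surgery), built from the pre-surgery clinical and laboratory data in section 4 where available. Confirm that the needed inputs are collected, including for ECMO patients.
3. Keep the 24, 48 and 72 h scores. In Statistical research, specify ANCOVA or a repeated-measures model with baseline SOFA as covariate, in place of the unadjusted tests for this outcome and not as an unadjusted change score.

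The cost is one more score per patient, a check that its inputs exist, some rewording and slightly more analysis work.
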